#### **7.1.3. Relationship of Adverse Events to Study Drug**

Related AEs are those for which the investigator answers “Related” to the question “Related to Study Treatment?” in the CRF. Events for which the investigator did not record relationship to study drug will be considered related to study drug. Data listings will show relationship as missing.

#### **7.1.4. Relationship of AEs to Study Procedure**

Adverse events for which “Yes” is marked for question “Related to Study Procedures?” in the eCRF will be identified and included in the AE listing.

#### **7.1.5. Serious Adverse Events**

Serious adverse events (SAEs) are those identified as serious in the clinical database. The clinical database will be reconciled with the SAE database from the Pharmacovigilance and Epidemiology (PVE) Department before database finalization.

## **7.1.6. Treatment-Emergent Adverse Events**

### **7.1.6.1. Definition of Treatment-Emergent Adverse Events**

Treatment-emergent adverse events (TEAEs) are defined as 1 or both of the following:

- Any AE with onset date on or after the study drug start date and no later than 30 days after permanent discontinuation of study drug, or
- Any AE leading to premature discontinuation of study drug.

### **7.1.6.2. Incomplete Dates**

If the onset date of the AE is incomplete and the AE stop date is not prior to the first dosing date of study drug, then the month and year (or year alone if month is not recorded) of onset determine whether an AE is treatment emergent. The event is considered treatment emergent if both of the following 2 criteria are met:

- The month and year of the AE onset date is the same as or after the month and year (or year) of the first dosing date of study drug, and
- The month and year of the AE onset date is the same as or before the month and year (or year) of the date corresponding to 30 days after the date of the last dose of study drug

An AE with completely missing onset and stop dates, or with the onset date missing and a stop date later than the first dosing date of study drug, will be considered to be treatment emergent. In addition, an AE with the onset date missing and incomplete stop date with the same or later month and year (or year alone if month is not recorded) as the first dosing date of study drug will be considered treatment emergent.

## **7.1.7. Summaries of Adverse Events and Deaths**

A brief summary of AEs will show overall and by Parts 1 and 2, the number and percentage of subjects who had:

- Any TEAE
- Any Grade 2, 3 or 4 TEAE
- Any Grade 3 or 4 TEAE
- Any study-drug-related TEAE
- Any Grade 2, 3 or 4 study-drug-related TEAE
- Any Grade 3 or 4 study-drug-related TEAE

- Any serious TEAE
- Any serious study-drug-related TEAE
- Any TEAE leading to premature study drug discontinuation
- Treatment-emergent death

Treatment-emergent death refers to death occurring between the first dose date and the last dose date plus 30 days (inclusive).

Summaries (number and percentage of subjects) of AEs (by SOC, and PT) will be provided overall and by Parts 1 and 2 using the Safety Analysis Set as follows:

- All TEAEs
- All Grade 2, 3, or 4 TEAEs
- Grade 3 or 4 TEAEs
- All study-drug-related TEAEs
- All Grade 2, 3, or 4 study-drug-related TEAEs
- All Grade 3 or 4 study-drug-related TEAEs
- All serious TEAEs
- All study-drug-related serious TEAEs
- All TEAEs that caused premature discontinuation from study drug

Multiple events will be counted only once per subject in each summary. For data presentation, SOC will be ordered alphabetically, and then by PT sorted by decreasing total frequency. For summaries by severity grade, the most severe event will be selected.

In addition to the by-treatment summaries, data listings will be provided for the following:

- All AEs
- Grade 3 and 4 AEs
- SAEs
- Adverse events leading to premature discontinuation of study drug
- Deaths report

## **7.1.8. Additional Analysis of Adverse Events**

### **7.1.8.1. Stage 3 Opportunistic Illnesses in HIV**

On an ongoing basis, AEs will be reviewed for events that might meet the definition of Stage 3 opportunistic illnesses in HIV that are indicative of an AIDS-Defining Diagnoses (see Protocol Appendix 6). The Gilead medical monitor will review the possible Stage 3 opportunistic illnesses and approve the events that meet the definition. Events that meet the Stage 3 opportunistic illness definition of an AIDS-Defining Diagnosis will be listed.

## **7.1.9. Fracture Events**

The preferred terms included in analysis for fracture events are defined based on the Standardized MedDRA Query (SMQ) of osteoporosis/osteopenia of fractures and HLGT of fractures from MedDRA. The lists of PTs selected by clinical review from all the PT terms under SMQ of osteoporosis/osteopenia fractures and HLGT of fractures are presented in [Appendix 4](#). Fracture events will be listed only.

## **7.2. Laboratory Evaluations**

Laboratory data collected during the study will be analyzed and summarized using both quantitative and qualitative methods. Summaries of laboratory data will be provided for the Safety Analysis Set and will include data collected up to the last dose of study drug plus 30 days for subjects who have permanently discontinued study drug. The analysis will be based on values reported in conventional units. When values are below the LOQ, they will be listed as such, and the closest imputed value will be used for the purpose of calculating summary statistics as specified in Section [3.6](#).

A by-subject listing for laboratory test results will be provided by subject ID number and visit in chronological order for hematology, serum chemistry, and urinalysis separately. Values falling outside of the relevant reference range and/or having a severity grade of 1 or higher on the Gilead Grading Scale for Severity of Adverse Events and Laboratory Abnormalities will be flagged in the data listings, as appropriate.

No formal statistical testing is planned.

### **7.2.1. Summaries of Numeric Laboratory Results**

Descriptive statistics (n, mean, standard deviation, median, Q1, Q3, minimum and maximum) will be provided overall and by Parts 1 and 2 for each laboratory test specified in the study protocol as follows:

- Baseline values
- Values at each postbaseline analysis window
- Change from baseline to each postbaseline analysis window

In the case of multiple values in an analysis window, data will be selected for analysis as described in Section 3.7.3.

Overall median (Q1, Q3) change from baseline in selected safety endpoints including the fasting lipid panel parameters and fasting glucose over time will be plotted.

#### 7.2.1.1. Metabolic Assessments

For the metabolic assessments (including total cholesterol, low density lipoprotein [LDL], high density lipoprotein [HDL], total cholesterol to HDL ratio, triglycerides, and glucose), only those measurements under fasting status will be summarized overall and by Parts 1 and 2.

In addition, the number and percentage of subjects who took lipid modifying medications at the study entry and initiated the medications during the study will be provided, respectively. A lipid modifying medication is defined as a medication with drug class “LIPID MODIFYING AGENTS” and CMDECOD containing the wording of “STATIN”.

A sensitivity analysis of fasting lipid tests (including total cholesterol, LDL, HDL, triglycerides, and total cholesterol to HDL ratio) will be performed by excluding subjects who took lipid modifying medications at study entry or initiated the medications during the study: baseline, Week 48. Only subjects with both baseline and Week 48 values will be included in the analysis.

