33) Lipid modifying medication analyses:

- Lipid modifying medication is defined to be the concomitant medication with any concomitant medication class “LIPID MODIFYING AGENTS” and CMDECOD contains wording of “STATIN” in the ADCM dataset.

- Subjects who took lipid modifying medications at study entry refer to the subjects who use of the lipid modifying agents at study day 1 (ie, the first dose date). More specifically, subjects with “Lipid Modifying Agent Use at Study Entry” include those subjects in Safety Analysis Set with: 1) any selected CM record with the start date  $\leq$  the first dose date, and 2) the end date of the selected CM record is ongoing or the end date of the selected CM record  $\geq$  the first dose date.
- Subjects who initiated lipid modifying medications during the study include the subjects in the Safety Analysis Set who didn’t take lipid modifying medications at study entry and met the following criteria: 1) for subjects who permanently discontinued study drug with any selected CM record started after the first dose date and on and prior to the last dose date; 2) for subjects who are still on study drug with any selected CM records started after the first dose date.
- For lipid modifying medications with the start date completely unknown, we assume the start date is on or before the first dose date, lipid modifying medication was considered as being taken at study entry if the end date is not prior to the first dose date (ie, the end date is on or after the first dose date, completely unknown, or ongoing).
- Lipid modifying medications with the start date prior to the first dose date and the end date completely unknown were considered as being taken at study entry.

34) Age for laboratory test reference range will be based on the age at the sample collection date.

35) For figures, if at a visit where n (sample size) for any treatment group  $< 5$ , data for that treatment group will not be displayed at the visit in figure, but all data will be included in the corresponding table summary.

36) For the PRO data, data up to 30 day after the last dose date for subjects who permanently discontinued of study drug will be summarized.

37) For PRO data, unless otherwise stated, multiple responses and out of range responses will be set to missing and missing responses will not be imputed.

Out of range value is determined based on the following table for within-range response values:

SF-36v2 Health Survey:

Question	Response	

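### The SAP's lipid-drug flag recognises only statins, so the lipid sensitivity analysis and medication counts do not match their label; dropping on-study statin starters may also understate a lipid rise

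*SAP*

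**What the plan says.** SAP 7.2.1.1 (Metabolic Assessments) gives the definition: "A lipid modifying medication is defined as a medication with drug class" LIPID MODIFYING AGENTS, joined by an 'and' to a second condition, that the coded name (CMDECOD) contains STATIN. Appendix 5 item 33 begins "Lipid modifying medication is defined to be the concomitant medication with any concomitant medication class" and attaches the same two conditions, so the programming will follow the main text.

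The flag drives two outputs in 7.2.1.1:

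- **Medication counts:** "the number and percentage of subjects who took lipid modifying medications at the study entry and initiated the medications during the study will be provided".
- **Sensitivity analysis:** total cholesterol, LDL, HDL, triglycerides and the total cholesterol to HDL ratio are re-analysed "excluding subjects who took lipid modifying medications at study entry or initiated the medications during the study: baseline, Week 48". The section adds: "Only subjects with both baseline and Week 48 values will be included in the analysis".

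For subjects who have stopped study drug, item 33 defines initiation as "any selected CM record started after the first dose date and on and prior to the last dose date", among those not already flagged at entry. The main laboratory summary (SAP 7.2 and 7.2.1) uses the Safety Analysis Set and makes no exclusion for lipid drugs.

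**The concern.** There are two separate issues.

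**Label and rule differ.** The tables speak of lipid modifying medications, but the rule finds only statins. A reader would take the sensitivity analysis to be free of lipid drugs and the counts to cover the whole class. Neither would be true if any subject takes only a non-statin lipid drug. Non-statins can act on triglycerides and HDL, which are among the five outcomes.

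**Selection after baseline.** Starting a statin happens after the first dose, and a lipid result is a plausible reason for it. Leaving those subjects out conditions the sample on something that may depend on the outcome. The trial has no comparator (Protocol 1.3), so the change from baseline is read directly and no parallel arm would reveal the selection. The risk is that a lipid rise after the switch looks smaller than it was.

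**Working it through.** The documents state no figure for this analysis, so there is none to reproduce. The first check is logical. The second scales the possible selection effect under stated assumptions.

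**1. What the flag catches.** I applied the STATIN condition to example generic names (my assumption; the documents name no non-statin lipid drug in use), each taken to be in the lipid class.

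| Coded name | Flagged? |
|---|---|
| atorvastatin, rosuvastatin, pravastatin, ezetimibe/simvastatin | yes |
| ezetimibe, fenofibrate, gemfibrozil, nicotinic acid, omega-3, colesevelam, evolocumab | no |

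So a user of only a non-statin stays in the analysis and out of the counts. The same holds for someone who starts only a non-statin on study: the initiator exclusion removes statin starters alone.

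**2. Size of the selection effect.** Assumptions, none of them in the documents:

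- a share q = 5% or 10% of subjects start a statin;
- the lipid change is normal, measured in SD units, with its mean without statins set to 0;
- starting follows a latent score that has correlation rho with that change;
- the statin lowers the Week 48 value by d SD.

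SAP 1.3 gives 64 subjects, so q corresponds to at most 0.05 x 64 = 3.2 or 0.10 x 64 = 6.4 people. The requirement for both values can only reduce the set.

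With z the (1 - q) normal quantile, the mean after dropping initiators shifts by -rho x phi(z)/(1 - q):

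- q = 5%: z = 1.645, phi(z) = 0.103, and 0.103/0.95 = 0.109.
- q = 10%: z = 1.282, phi(z) = 0.1755, and 0.1755/0.90 = 0.195.

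| rho | q = 5% | q = 10% |
|---|---|---|
| 0 (unrelated) | 0 | 0 |
| 0.3 | -0.03 SD | -0.06 SD |
| 0.6 | -0.07 SD | -0.12 SD |
| 1 (exactly the largest risers) | -0.11 SD | -0.20 SD |

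The median, at the 0.5 x (1 - q) quantile, shifts less: in the worst case -0.06 SD (5%) and -0.13 SD (10%). A simulation of the same model agrees with the table of means to within 0.003 SD.

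**3. Compared with the main summary.** The main summary keeps initiators, but their Week 48 values are then taken on the statin, so its mean shifts by -q x d. At q = 10% and d = 1 SD that is -0.10 SD. The sensitivity mean is -0.06 SD at rho = 0.3 (higher than the main result) and -0.20 SD at rho = 1 (lower). The two are equal where rho = 0.10/0.195 = 0.51. The order of the two results therefore depends on quantities that the documents do not give.

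**The case against.** The strongest reply is that the rule is explicit and identical in two places, so it is a choice and not a slip, and that little hangs on it. Much of this stands:

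- The main lipid summary has no drug exclusion.
- Treatment-emergent graded abnormalities (SAP 7.2.2.1 and 7.2.2.2) use any post-baseline value, so a graded Week 24 rise still counts if a statin follows.
- Concomitant non-antiretroviral drugs are summarised by preferred name and listed (SAP 7.5.2), so non-statin users remain visible.
- Lipids are not a named objective or endpoint, and no test is planned.
- No document shows that any subject used a non-statin lipid drug.

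This limits the consequence but does not make the label correct.

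A reader might go further and infer that the exclusion removes the subjects whose lipids rose most. The documents do not support that. They set no lipid threshold for starting a statin and give no lipid data on initiators. They also leave open a route unrelated to an on-study rise: Protocol Table 4-2 requires simvastatin and lovastatin to be stopped at least 30 days before Day 1, while Table 5-1 permits atorvastatin with caution. A subject who starts a replacement after the first dose would count as an initiator.

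A reader might also infer that most of a true rise would vanish. Assuming an LDL rise of 0.30 mmol/L with SD 0.60, removal of exactly the top 10% leaves 0.30 - 0.60 x 0.195 = 0.18, and removal of the top 20% leaves 0.30 - 0.60 x 0.35 = 0.09. Those figures require perfect selection, many initiators and a small assumed mean, and a rise still shows.

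**Conclusion.** The definition point holds on the text alone: the flag is narrower than its name, and both the sensitivity analysis and the counts inherit the gap. How many subjects it affects is unknown.

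The selection point holds as a risk. The sensitivity analysis may understate a rise, by nothing if starting a statin is unrelated to it and by about 0.1 to 0.2 SD of the mean in the worst case, given the assumed 5 to 10% initiators. Direction and size relative to the main summary are not established. Neither planned analysis avoids the problem, since one drops initiators and the other uses values taken on treatment.

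The consequence is confined to a descriptive safety sensitivity analysis and its medication table. The primary conclusion is untouched, and this is a minor, worthwhile correction.

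**What to change.** 1. Delete the STATIN condition in SAP 7.2.1.1 and in Appendix 5 item 33, so that drug class alone defines the flag. The cost is one line of code and perhaps a few more subjects excluded. If statins alone are intended, keep the rule and label the flag and tables statin use.
2. Add one row that excludes only users at study entry. List on-study initiators separately with start date and their Day 1, Week 24 and Week 48 fasting values. Keep the current exclusion as a second row. This costs one table row and one short listing.
3. Do not carry forward values from before initiation. Fasting lipids are scheduled only at Day 1, Week 24 and Week 48 (Protocol 6.2.2, 6.3.1 and Appendix 2). On that schedule, someone who starts before Week 24 would be given a change of zero by construction, and a later starter would bring a Week 24 value into a Week 48 analysis.

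If the SAP is already final, its Introduction provides for recording such changes in the clinical study report.

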#### 7.2.1.2. Calcium Corrected for Albumin

Calcium corrected for albumin will be calculated and summarized overall and by Parts 1 and 2. The following formula will be used when both serum calcium and albumin results for a given blood draw are available and serum albumin value is < 4.0 g/dL.

Calcium corrected for albumin (mg/dL) = serum calcium (mg/dL) + 0.8 x (4.0 - albumin (g/dL)).  
Toxicity grading for calcium will be applied based on the corrected values.

### 7.2.2. Graded Laboratory Values

The criteria specified in the study protocol will be used to grade laboratory results as Grade 0, mild (Grade 1), moderate (Grade 2), severe (Grade 3) or potentially life threatening (Grade 4). Grade 0 includes all values that do not meet criteria for an abnormality of at least Grade 1. Some laboratory tests have criteria for both increased and decreased levels; analyses for each direction (i.e., increased, decreased) will be presented separately.

For triglycerides, LDL, and cholesterol, the protocol specified toxicity grade scale is for fasting test values, so nonfasting lipid results (or lipid results without known fasting status) will not be graded or summarized by toxicity grades.

If there is any laboratory toxicity grading scale overlapping with normal reference ranges (eg, Grade 1 scale overlaps with normal reference ranges), laboratory values within normal range will be grade 0, except lipid tests.

#### 7.2.2.1. Treatment-Emergent Laboratory Abnormalities

Treatment-emergent laboratory abnormalities are defined as values that increase at least one toxicity grade from baseline at any time post-baseline up to and including the date of last dose of study drug plus 30 days for subjects who permanently discontinued study drug. If the relevant baseline laboratory data are missing, then any abnormality of at least Grade 1 will be considered treatment emergent.

For serum glucose, fasting glucose and nonfasting glucose are graded based on different grading criteria as specified in the protocol. Treatment-emergent laboratory abnormalities will be summarized for fasting glucose. Since nonfasting glucose was not assessed at baseline, the maximum postbaseline grade instead of treatment-emergent laboratory abnormalities will be summarized.

#### 7.2.2.2. Summaries of Laboratory Abnormalities

The following summaries (number and percentage of subjects) of laboratory abnormalities will be provided overall and by Parts 1 and 2 (subjects categorized according to most severe abnormality grade):

- Treatment-emergent laboratory abnormalities
- Treatment-emergent Grade 3 and 4 laboratory abnormalities

For all summaries of laboratory abnormalities, the denominator is the number of subjects with non-missing post-baseline values. A listing of all graded laboratory abnormalities and all Grade 3 or Grade 4 laboratory abnormalities will be provided.

#### 7.2.3. Liver-related Laboratory Evaluations

The number and percentage of subjects will be summarized overall and by Parts 1 and 2 for the following liver-related laboratory tests and categories:

- AST: (a) > 3 x Upper limit of normal (ULN), (b) > 5 x ULN, (c) > 10 x ULN, (d) > 20 x ULN
- ALT: (a) > 3 x ULN, (b) > 5 x ULN, (c) > 10 x ULN, (d) > 20 x ULN
- AST or ALT: (a) > 3 x ULN, (b) > 5 x ULN, (c) > 10 x ULN, (d) > 20 x ULN
- Total bilirubin: (a) > 1 x ULN, (b) > 2 x ULN
- Alkaline phosphatase (ALP) > 1.5 x ULN
- AST or ALT > 3 x ULN and total bilirubin: (a) > 1.5 x ULN, (b) > 2 x ULN
- AST or ALT > 3 x ULN and total bilirubin > 2 x ULN and ALP < 2 x ULN

The summary will include data from all the postbaseline visits up to 30 days after the last dose of study drug. For individual laboratory tests, subjects will be counted once based on the most severe postbaseline values. For both the composite endpoint of AST or ALT and total bilirubin, and the composite endpoint of AST or ALT, total bilirubin, and ALP, subjects will be counted once when the criteria are met at the same postbaseline visit date. The denominator is the number of subjects in the Safety Analysis Set with nonmissing postbaseline value of the tests in evaluation at the same postbaseline visit date.

Subjects with AST or ALT > 3 x ULN will also be listed.

### **7.3. Renal Safety Analyses**

#### **7.3.1. Serum Creatinine**

The baseline, postbaseline and change from baseline in serum creatinine at each visit will be summarized overall and by Parts 1 and 2 for each visit using descriptive statistics.

The median (Q1, Q3) of change from baseline in observed serum creatinine over time will be plotted.

#### **7.3.2. Estimated Glomerular Filtration Rate**

##### **7.3.2.1. Estimated Glomerular Filtration Rate: Cockcroft-Gault**

The Cockcroft-Gault formula will be used to calculate eGFRCG:

$$\text{eGFR}_{\text{CG}} \text{ (mL/min)} = \frac{[(140 - \text{age (years)}) \times \text{weight (kg)} \times (0.85 \text{ if female})]}{(\text{SCr (mg/dL)} \times 72)},$$

where weight is total body mass in kilograms, and SCr is serum creatinine.

Summary of baseline, post-baseline, and change from baseline in eGFRCG will also be provided overall and by Parts 1 and 2.

Median (Q1, Q3) change from baseline in eGFRCG over time will be plotted.

##### **7.3.2.2. Estimated Glomerular Filtration Rate: CKD-EPI (cystatin C)**

The CKD-EPI (cystatin C) formula will be used to calculate eGFRCKD EPI:

$$\text{eGFR}_{\text{CKD EPI}} \text{ (mL/min/1.73 m}^2\text{)} = 133 \times \min(\text{Scys}/0.8, 1)^{0.499} \times \max(\text{Scys}/0.8, 1)^{1.328} \times 0.996^{\text{Age}} [\times 0.932 \text{ if female}],$$

where Scys is serum cystatin C (mg/L), min (Scys/0.8,1) indicates the minimum of Scys/κ or 1, and max (Scys/0.8,1) indicates the maximum of Scys/κ or 1.

Only baseline values will be summarized. See Section 5.2 for details.

